5.2 Tremelimumab

Tremelimumab will be supplied by AstraZeneca as a 400-mg vial solution for infusion after dilution. The solution contains 20 mg/mL of tremelimumab, 20 mM histidine/histidine hydrochloride, 222 mM trehalose dihydrate, 0.02% (w/v) polysorbate 80, and 0.27 mM disodium edetate dihydrate (EDTA); it has a pH of 5.5. The nominal fill volume is 20 mL. Investigational product vials are stored at 2°C to 8°C (36°F to 46°F) and must not be frozen. Tremelimumab must be used within the individually assigned expiry date on the label.

Preparation of tremelimumab doses for administration with an IV bag

The dose of tremelimumab for administration must be prepared by the Investigator's or site's designated IP manager using aseptic technique. Total time from needle puncture of the tremelimumab vial to the start of administration should not exceed:

- 24 hours at 2°C to 8°C (36°F to 46°F)
- 4 hours at room temperature

It is recommended that the prepared final IV bag be stored in the dark at 2°C-8°C (36°F-46°F) until needed. If storage time exceeds these limits, a new dose must be prepared from

new vials. The refrigerated infusion solutions in the prepared final IV bag should be equilibrated at room temperature for about 2 hours prior to administration. Tremelimumab does not contain preservatives and any unused portion must be discarded.

No incompatibilities between tremelimumab and polyvinylchloride or polyolefin IV bags have been observed. Doses of 75 mg tremelimumab for patients >30 kg will be administered using an IV bag containing 0.9% (w/v) saline, with a final tremelimumab concentration ranging from 0.1 mg/mL to 10 mg/mL, and delivered through an IV administration set with a 0.2 μ m or 0.22 μ m in-line filter. Remove 3.8 mL of IV solution from the IV bag prior to addition of tremelimumab. Next, 3.8 mL of tremelimumab (i.e., 75 mg of tremelimumab) is added to the IV bag such that final concentration is within 0.1 mg/mL to 10 mg/mL (IV bag volumes 50 to 500 mL). Mix the bag by gently inverting to ensure homogeneity of the dose in the bag.

A fixed dose of 75mg of Tremelimumab will be used. Tremelimumab will be administered at room temperature (approximately 25°C) by controlled infusion via an infusion pump into a peripheral or central vein. Following preparation of tremelimumab, the entire contents of the IV bag should be administered as an IV infusion over approximately 60 minutes, using a 0.2, or 0.22- μ m in-line filter. Longer infusions up to 8 hours are allowed if interruptions are necessary (see below).

The IV line will be flushed with a volume of 0.9% (w/v) saline equal to the priming volume of the infusion set used after the contents of the IV bag are fully administered, or complete the infusion according to institutional policy to ensure the full dose is administered and document if the line was not flushed.

Standard infusion time is 1 hour. However, if there are interruptions during infusion, the total allowed time should not exceed 8 hours at room temperature. The table below summarizes time allowances and temperatures.

Tremelimumab hold and infusion times

Maximum time from needle puncture to start of administration	4 hours at room temperature, 24 hours at 2°C to 8°C
Maximum time for IV bag infusion, including interruptions	8 hours at room temperature

In the event that either preparation time or infusion time exceeds the time limits outlined in the table, a new dose must be prepared from new vials. Tremelimumab does not contain preservatives, and any unused portion must be discarded.

5.3 Monitoring of dose administration

Patients will be monitored before, during and after the infusion with assessment of vital signs as outlined in section 10.

In the event of a \leq Grade 2 infusion-related reaction, the infusion rate of study drug may be decreased by 50% or interrupted until resolution of the event and re-initiated at 50% of the initial rate until completion of the infusion. For patients with a \leq Grade 2 infusion-related reaction, subsequent infusions may be administered at 50% of the initial rate. Acetaminophen and/or an antihistamine (e.g., diphenhydramine) or equivalent medications per institutional standard may be administered at the discretion of the investigator. If the infusion-related reaction is \geq Grade 3 or higher in severity, study drug will be discontinued.

As with any antibody, allergic reactions to dose administration are possible. Appropriate drugs and medical equipment to treat acute anaphylactic reactions must be immediately available, and study personnel must be trained to recognize and treat anaphylaxis. The study site must have immediate access to emergency resuscitation teams and equipment in addition to the ability to admit patients to an intensive care unit if necessary.

6.1 CRITERIA FOR SUBJECT ELIGIBILITY

6.2 Subject Inclusion Criteria

For inclusion in the study, patients should fulfill the following criteria:

1. Age \geq 18 years at time of informed consent
2. Body weight $>$ 30 kg
3. Histologically or cytologically confirmed small cell carcinoma, squamous cell carcinoma or adenocarcinoma (confirmed at MSKCC) of the bladder, ureter, urethra, urachus, or renal pelvis. Patients with squamous cell carcinoma and adenocarcinoma are required to have a predominant squamous or adenocarcinoma component as reviewed by the pathologist at MSKCC. However, if any element of small cell or neuroendocrine differentiation is present, the patients will be classified as small cell/neuroendocrine.
4. Confirmation of availability of sufficient tissue from a prior surgery for correlative studies is required prior to enrollment. Patients must have representative non-TCC or the urothelial tract FFPE archival tumor specimens (tumor blocks or 30 unstained slides; preference for tumor blocks). These samples may be submitted between the time of consent and the start of treatment. Patients with $<$ 30 slides may be enrolled after discussion with the principal or co-principal investigators, see Section 9.5.2 for more details.
5. Clinical evidence of metastatic (T4b, any N; any T, N2-3; M1) disease.
6. Life expectancy of 12 weeks of greater based on assessment by the treating investigator.
7. Evidence of measurable disease by RECIST 1.1.
8. Patients with small cell carcinoma must have progressed after at least one prior systemic therapy. Patients with squamous cell carcinoma or adenocarcinoma may be previously

untreated or have progressed after prior systemic therapy. Chemotherapy administered in conjunction with primary radiation as a radio-sensitizer WILL be counted as a systemic chemotherapy regimen. NOTE: There is no maximum number of prior treatments allowed.

9. Patients with brain metastases are allowed onto the study as long as patients have completed their treatment for brain metastasis, no longer require corticosteroids, and are asymptomatic. Subjects with neurological symptoms should undergo a head CT scan or brain MRI to exclude brain metastasis, at the discretion of the treating physician.

10. Eastern Cooperative Oncology Group (ECOG) performance status of 0-1

11. Adequate normal organ and marrow function as defined below:

- Hemoglobin \geq 9.0 g/dL
- Absolute neutrophil count (ANC) $\geq 1.0 \times 10^9/L$ (≥ 1000 per mm 3)
- Platelet count $\geq 100 \times 10^9/L$ ($\geq 100,000$ per mm 3)
- Serum bilirubin $\leq 1.5 \times$ institutional upper limit of normal (ULN) ($\leq 3 \times$ institutional ULN in patients with Gilbert's syndrome)
- AST (SGOT)/ALT (SGPT) $\leq 2.5 \times$ institutional ULN unless liver metastases are present, in which case it must be $\leq 5 \times$ ULN
- Calculated creatinine clearance > 30 mL/min by the Cockcroft-Gault formula (Cockcroft and Gault 1976) or by 24-hour urine collection for determination of creatinine clearance:

Males:

$$\text{Creatinine CL (mL/min)} = \frac{\text{Weight (kg)} \times (140 - \text{Age})}{72 \times \text{serum creatinine (mg/dL)}}$$

Females:

$$\text{Creatinine CL (mL/min)} = \frac{\text{Weight (kg)} \times (140 - \text{Age})}{72 \times \text{serum creatinine (mg/dL)}} \times 0.85$$

12. Evidence of post-menopausal status or negative serum pregnancy test for female pre-menopausal patients. Women will be considered post-menopausal if they have been amenorrheic for 12 months without an alternative medical cause. The following age-specific requirements apply:

- Women <50 years of age would be considered post-menopausal if they have been amenorrheic for 12 months or more following cessation of exogenous hormonal treatments and if they have luteinizing hormone and follicle-stimulating hormone levels in the post-menopausal range for the institution or underwent surgical sterilization (bilateral oophorectomy or hysterectomy).

- Women \geq 50 years of age would be considered post-menopausal if they have been amenorrheic for 12 months or more following cessation of all exogenous hormonal treatments, had radiation-induced menopause with last menses $>$ 1 year ago, had chemotherapy-induced menopause with last menses $>$ 1 year ago, or underwent surgical sterilization (bilateral oophorectomy, bilateral salpingectomy or hysterectomy).

13. Female patients of reproductive potential and non-sterilized males who are sexually active with a female partner of childbearing potential must be willing to adhere to the following restrictions:

- Females of reproductive potential who are sexually active with a non-sterilized male partner must agree to use at least 1 **highly** effective method of contraception (Table 3) from the time of screening until 180 days after the last dose of durvalumab + tremelimumab combination therapy or 90 days after the last dose of durvalumab monotherapy. Cessation of birth control after this point should be discussed with a responsible physician. Periodic abstinence, the rhythm method, and the withdrawal method are not acceptable methods of birth control. It is strongly recommended that non-sterilized male partners of a female patient must use male condom plus spermicide throughout this period. Not engaging in sexual activity for the total duration of the drug treatment and the drug washout period is an acceptable practice.
- Non-sterilized males who are sexually active with a female partner of childbearing potential must use a male condom plus spermicide from screening through 180 days after receipt of the final dose of durvalumab + tremelimumab combination therapy or 90 days after receipt of the final dose of durvalumab monotherapy. Periodic abstinence, the rhythm method, and the withdrawal method are not acceptable methods of birth control. Not engaging in sexual activity is an acceptable practice. Male patients should refrain from sperm donation throughout this period. It is strongly recommended that female partners (of childbearing potential) of male patients to also use a highly effective method of contraception (Table 3) throughout this period.
- Highly effective methods of contraception, defined as one that results in a low failure rate (i.e., less than 1% per year) when used consistently and correctly are described in Table 3.

Table 3. Highly effective methods of contraception (<1% failure rate)

Barrier/Intrauterine methods	Hormonal Methods

 • Copper T intrauterine device • Levonorgestrel-releasing intrauterine system (e.g., Mirena®)^a 	
 • Implants: Etonogestrel-releasing implants: e.g. Implanon® or Norplant® • Intravaginal: Ethinylestradiol/etonogestrel-releasing intravaginal devices: e.g. NuvaRing® • Injection: Medroxyprogesterone injection: e.g. Depo-Provera® • Combined Pill: Normal and low dose combined oral contraceptive pill • Patch: Norelgestromin/ethinylestradiol-releasing transdermal system: e.g. Ortho Evra® • Minipill: Progesterone based oral contraceptive pill using desogestrel: Cerazette® is currently the only highly effective progesterone based pill

^a This is also considered a hormonal method

14. Subject is willing and able to comply with the protocol for the duration of the study including undergoing treatment and scheduled visits and examinations including follow up.

6.3 Subject Exclusion Criteria

Subjects should not enter the study if any of the following exclusion criteria are fulfilled:

1. Previous enrollment in the present study
2. Participation in another clinical study with an investigational product during the last 14 days
3. Mean QT interval corrected for heart rate (QTc) ≥ 470 ms calculated from 3 electrocardiograms (ECGs) using Fredericia's Correction
4. Any previous treatment with a PD-1 or PD-L1 inhibitor, including durvalumab or an anti-CTLA-4, including tremelimumab
5. Receipt of the last dose of anti-cancer therapy (chemotherapy, immunotherapy, endocrine therapy, targeted therapy, biologic therapy, tumor embolization, monoclonal antibodies, other investigational agent) < 21 days prior to enrollment.
6. Major surgery within 28 days of starting study treatment. There is no minimum time requirement for minor procedures such as biopsy or vascular access placement.
7. Radiation within 14 days of starting study treatment

8. Current or prior use of immunosuppressive medication within 14 days before the first dose of durvalumab or tremelimumab. The following are exceptions to this criterion:
 - Intranasal, inhaled, topical steroids, or local steroid injections (e.g., intra articular injection)
 - Systemic corticosteroids at physiologic doses not to exceed <<10 mg/day>> of prednisone or its equivalent
 - Steroids as premedication for hypersensitivity reactions (e.g., CT scan premedication)
9. Any unresolved toxicity from previous anti-cancer therapy must have resolved to at least \leq Grade 1 (or baseline) at time of enrollment.

Patients with irreversible toxicity that is not reasonably expected to be exacerbated by treatment with durvalumab and tremelimumab may be included after consultation with the Principal Investigator or Co-Principal Investigator (e.g. alopecia, hearing loss, peripheral neuropathy).
10. Active or prior documented autoimmune or inflammatory disorders (including inflammatory bowel disease [e.g., colitis or Crohn's disease], diverticulitis, celiac disease, systemic lupus erythematosus, Sarcoidosis syndrome, or Wegener syndrome [granulomatosis with polyangiitis, Graves' disease, rheumatoid arthritis, hypophysitis, uveitis, etc]). The following are exceptions to this criterion:
 - Patients with vitiligo or alopecia
 - Patients with hypothyroidism (eg, following Hashimoto syndrome) stable on hormone replacement
 - Any chronic skin condition that does not require systemic therapy
 - Patients without active autoimmune disease in the last 5 years may be included but only after consultation with the study physician
 - Patients with diverticulosis
 - Patients with celiac disease controlled by diet alone
11. History of primary immunodeficiency
12. History of allogeneic organ transplant
13. History of hypersensitivity to durvalumab, tremelimumab or any excipient
14. Uncontrolled intercurrent illness, including but not limited to, ongoing or active infection, symptomatic congestive heart failure, uncontrolled hypertension, unstable angina pectoris, cardiac arrhythmia, interstitial lung disease, serious chronic gastrointestinal conditions associated with diarrhea, or psychiatric illness/social situations that would limit compliance with study requirement, substantially increase risk of incurring AEs or compromise the ability of the patient to give written informed consent.
15. Active infection including **tuberculosis** (clinical evaluation that includes clinical history, physical examination and radiographic findings, and TB testing in line with local practice),

hepatitis B (known positive HBV surface antigen (HBsAg) result), **hepatitis C**, or **human immunodeficiency virus** (positive HIV 1/2 antibodies). Patients with a past or resolved HBV infection (defined as the presence of hepatitis B core antibody [anti-HBc] and absence of HBsAg) are eligible. Patients positive for hepatitis C (HCV) antibody are eligible only if polymerase chain reaction is negative for HCV RNA.

16. History of leptomeningeal carcinomatosis
17. Receipt of live attenuated vaccination within 30 days prior to study entry or within 30 days of receiving durvalumab or tremelimumab. Inactivated vaccines, such as the injectable influenza vaccine, are permitted.
18. Any condition that, in the opinion of the investigator, would interfere with evaluation of study treatment or interpretation of patient safety or study results
19. Malignancies other than the disease under study within 5 years prior to Cycle 1, Day 1, with the exception of those with a negligible risk of metastasis or death and with expected curative outcome (such as adequately treated carcinoma in situ of the cervix, basal or squamous cell skin cancer, localized prostate cancer treated surgically with curative intent, or ductal carcinoma in situ treated surgically with curative intent) or undergoing active surveillance per standard-of-care management (e.g. prostate cancer with Gleason score ≤ 6 , and prostate-specific antigen [PSA] ≤ 10 mg/mL, etc).
20. Patients should agree to not donate blood while participating in this study or for at least 90 days following the last infusion of durvalumab or tremelimumab
21. Female patients who are pregnant or breastfeeding or male or female patients of reproductive potential who are not willing to employ effective birth control from screening to 90 days after the last dose of durvalumab monotherapy or 180 days after the last dose of durvalumab + tremelimumab combination therapy.

7.0 RECRUITMENT PLAN

Eligible patients with non-TCC of the urothelial tract will be recruited from the Genitourinary Oncology and Urology Services at MSKCC. Every attempt will be made to recruit women and minorities to participate in this study. Participation is voluntary. The consenting physician will inform patients of their diagnosis, current treatment options including standard treatment, and the risks, benefits, and experimental nature of this treatment program.

8.1 PRETREATMENT EVALUATION

The following studies must be completed within 14 days prior to study registration/ enrollment (unless otherwise indicated):

- Informed consent (within 28 days)
- Review of eligibility criteria
- Medical history and demographics, including tobacco and alcohol use

- Complete physical exam (with height measured at screening only)
- ECOG Performance Status
- Vitals signs including temperature, blood pressure, respiratory rate, heart rate, weight, and height
- 12-lead ECG (in triplicate [2-5 minutes apart])
- Submission of archival tumor tissue. Patients without archival tumor tissue may be enrolled after discussion with the principal investigator. Repeat biopsies purely for investigational purposes for this study will not be performed. See section 9.5.2 for additional details.
- Review of prior/concomitant medications
- Appropriate radiographic diagnostic procedures (for example CT scan of chest and CT or MRI of the abdomen & pelvis) for evaluation of measurable disease at baseline within 28 days of registration.
- Clinical laboratory tests for:
 - CBC (see Table 4)
 - Clinical chemistry panel (see Table 5)
 - TSH (free T3 and free T4 only if TSH is abnormal)
 - Coagulation (PT, PTT, INR)
 - Estimated Creatinine Clearance using the Cockcroft-Gault formula
 - Serum pregnancy test (for women of childbearing potential only)
 - Hepatitis serologies (Hepatitis B surface antigen, hepatitis B core antibody, hepatitis C antibody) and HIV antibody screen within 28 days
 - Urinalysis (see Table 6)
- Research bloods as outlined in section 9 and per MSKCC standard operating procedures

Table 4. Complete blood count (CBC)

Basophils	Mean corpuscular volume
Eosinophils	Monocytes
Hematocrit	Neutrophils
Hemoglobin	Platelet count
Lymphocytes	Red blood cell count
Mean corpuscular haemoglobin	Total white cell count
Mean corpuscular haemoglobin concentration	

Table 5. Clinical chemistry (Serum or Plasma) Laboratory Tests

Albumin	Creatinine
Alkaline phosphatase	Glucose
Alanine aminotransferase	Lipase*
	Magnesium*
Amylase*	Potassium
Aspartate aminotransferase	Sodium
Bicarbonate	Total bilirubin ^a
Calcium	Total protein
Chloride	Urea or blood urea nitrogen, depending on local practice

^a If Total bilirubin is $\geq 1.5 \times \text{ULN}$ (and no evidence of Gilbert's syndrome) then fractionate into direct and indirect bilirubin

*These tests are not part of the standard MSKCC comprehensive metabolic panel and will need to be ordered separately.

Table 6.

Urinalysis Tests^a

Bilirubin	pH
Blood	Protein
Glucose	Specific gravity
Ketones	Colour and appearance

^a Microscopy should be used as appropriate to investigate white blood cells and use the high power field for red blood cells

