12.1 CRITERIA FOR THERAPEUTIC RESPONSE/OUTCOME ASSESSMENT

Patients will be assessed every cycle by physical examination for response for disease progression. Patients will have appropriate radiographic diagnostic procedures (CT scan of chest and CT or MRI of abdomen and pelvis) for evaluation of measurable disease at baseline within 28 days of initiation of the study. Imaging will be repeated to evaluate the disease every 2 cycles while patients are on study.

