12.2 Response Criteria

The response evaluation criteria in solid tumors (RECIST 1.1) will be used as presented in Appendix 4. The immune-related RECIST (irRECIST) criteria will also be used as a response

assessment as described in Appendix 5.

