Bone lesions: Bone scan, positron emission tomography (PET) scan, or plain films are not considered adequate imaging techniques to measure bone lesions. However, these techniques can be used to confirm the presence or disappearance of bone lesions.

- Lytic bone lesions or mixed lytic-blastic lesions, with identifiable soft tissue components, that can be evaluated by cross-sectional imaging techniques such as CT or MRI can be considered measurable lesions if the soft tissue component meets the definition of measurability described above.
- Blastic bone lesions are non-measurable.

Cystic lesions: Lesions that meet the criteria for radiographically defined simple cysts should not be considered malignant lesions (neither measurable nor non-measurable) since they are, by definition, simple cysts.

- Cystic lesions thought to represent cystic metastases can be considered measurable lesions if they meet the definition of measurability described above. However, if non-cystic lesions are present in the same patient, these are preferred for selection as target lesions.

Lesions with prior local treatment: Tumor lesions situated in a previously irradiated area, or in an area subjected to other loco-regional therapy, are usually not considered measurable unless there has been demonstrated progression in the lesion. Study protocols should detail the conditions under which such lesions would be considered measurable.

II. Target Lesions: Specifications by Methods of Measurements

A. Measurement of Lesions

All measurements should be recorded in metric notation, using calipers if clinically assessed. All baseline evaluations should be performed as close as possible to the treatment start and never more than 4 weeks before the beginning of the treatment.

B. Method of Assessment

The same method of assessment and the same technique should be used to characterize each identified and reported lesion at baseline and during study. Imaging-based evaluation should always be the preferred option.

Clinical Lesions. Clinical lesions will only be considered measurable when they are superficial and ≥ 10 mm in diameter as assessed using calipers (e.g., skin nodules). For the case of skin lesions, documentation by color photography, including a ruler to estimate the size of the lesion, is suggested.

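### The baseline scan is timed from three different events, and a target lesion can be irradiated between that scan and first dose

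*Combined protocol and SAP*

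**What the plan says.** The protocol times the baseline scan in four places:

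- Section 8.1 sets a general rule, "The following studies must be completed within 14 days prior to study registration/ enrollment", with imaging as an exception, "for evaluation of measurable disease at baseline within 28 days of registration".
- Section 12.1 requires imaging "within 28 days of initiation of the study". I find no definition of that event.
- The section 10 schedule puts the scans in a 28-day screening column without naming a reference event.
- Appendix 4 (II.A) says baseline evaluations are "never more than 4 weeks before the beginning of the treatment". Section 12.2 makes this binding: "The response evaluation criteria in solid tumors (RECIST 1.1) will be used as presented in Appendix 4".

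The section 6.3 exclusions use two further reference points. Radiotherapy is "Radiation within 14 days of starting study treatment"; prior anticancer drugs are excluded if the last dose was "< 21 days prior to enrollment".

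Appendix 4 measures partial response as a 30% fall from the baseline sum of target-lesion diameters. It also says that lesions in an already irradiated or locally treated area are usually not measurable unless they have progressed, and that study protocols should spell out the conditions. I find no such detail in this protocol.

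**The concern.** There are two separate problems.

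First, the anchors conflict. A site working from 8.1 can hold a scan that is valid at registration but more than 4 weeks old at first dose. The protocol uses the treatment anchor elsewhere: section 9.2 ties the retreatment baseline to the restart of treatment.

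Second, the scan window is longer than the radiotherapy exclusion, and nothing requires the scan to follow the last prior treatment. If a measured lesion is irradiated before first dose, its shrinkage is counted against a baseline taken before the radiation. In a single-arm trial there is no control group to show the bias, so the shrinkage would be credited to the study drugs. The decision rule is sensitive to single patients: one response in 13 opens stage 2, and four in 27 make the therapy promising.

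**Working it through.** **Day counts.** Let *g* be the days from registration to first dose. The documents give no maximum, so 0, 3, 7 and 14 days are assumed for illustration.

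- Oldest scan allowed by 8.1, counted back from first dose: 28 + *g*.
- Last radiotherapy allowed by 6.3: day −15 before first dose, so it can follow the scan by 28 + *g* − 15 = 13 + *g* days (one more if day −14 is read as allowed).
- Last prior drug dose allowed: 21 days before enrollment, which 8.1 treats as the same event as registration. It can follow the scan by 28 − 21 = 7 days, whatever *g* is.

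| *g* (assumed) | Oldest scan at first dose | Over the 4-week limit by | Radiotherapy after scan, up to | Drug dose after scan, up to |
|---|---|---|---|---|
| 0 | 28 d | 0 | 13 d | 7 d |
| 3 | 31 d | 3 d | 16 d | 7 d |
| 7 | 35 d | 7 d | 20 d | 7 d |
| 14 | 42 d | 14 d | 27 d | 7 d |

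If the scan is only re-anchored to 28 days before first dose, the 4-week limit is met, but radiotherapy can still follow the scan by 28 − 15 = 13 days and a drug dose by max(0, 7 − *g*) days. Re-anchoring alone does not close the second problem.

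**The plan's own design.** Inputs from section 14.2: null rate 5%, target rate 20%, 13 then 14 patients, continue with at least 1 response, promising with at least 4 of 27. The probability of a positive trial is the sum over x ≥ 1 of P(X₁ = x) · P(X₂ ≥ 4 − x), with X₁ ~ Bin(13, p) and X₂ ~ Bin(14, p).

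- At p = 0.05: 0.0416. At p = 0.20: 0.8011. Chance of stopping at stage 1 under the null: 0.95¹³ = 0.513.
- A search for the minimax design returns the same 13/27 rule. The sample size is reproduced and is not in question.

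**Effect of exactly one spurious confirmed responder, the others at 5%.**

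- In stage 1: the futility rule is passed by that patient alone, and 3 of the other 26 are needed. P(Bin(26, 0.05) ≥ 3) = 0.139.
- In stage 2: at least one true response is needed among the first 13, then 3 in total among the 26 others. The result is 0.126.
- The observed response rate rises by 1/27 = 3.7 percentage points in either case.

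**Range, because the frequency is unknown.** With an assumed per-patient chance *c* of a spurious response, the effective rate is 0.05 + 0.95*c*. For *c* = 1%, 2% and 5%, the false-positive risk is 7.0%, 10.7% and 25.6%. These are illustrations, not estimates.

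**How large the irradiated lesion must be.** If it makes up a share *w* of the baseline sum, shrinks by a fraction *s*, and the other target lesions do not change, partial response needs *w* × *s* ≥ 0.30. Even if the lesion disappears (*s* = 1), it must be at least 30% of the sum.

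**The case against.** The strongest reply is that the safeguards already exist.

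- **The 4-week limit is in the plan.** Section 12.2 adopts Appendix 4, so a site dosing on a 35-day-old scan is in breach of the protocol. This stands. A reader might infer from 8.1 that the plan has no limit relative to treatment; the documents do not support that. It is a contradiction to reconcile.
- **Previously treated patients must have progressed.** Section 6.2 item 8 requires progression after prior systemic therapy, and the drug window is 7 days at most. This stands, and it makes the drug route minor. It does not address radiotherapy.
- **Irradiated lesions are usually not measurable.** This stands in part. A reader might infer that a lesion measured first and irradiated afterwards is definitely a valid target. Appendix 4 does not say so. It is unclear on this sequence, because it speaks of earlier irradiation in rules for classifying lesions at baseline.
- **Responses must be confirmed.** The endpoint is confirmed response (section 1.0), with a repeat assessment at least 4 weeks later (12.3). The sum can include up to five target lesions, and new lesions or non-target progression defeat a response. This stands and makes a spurious response less likely, but it does not rule out one where a single lesion dominates the sum.

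A reader might also infer that tumor growth between an old scan and first dose materially shifts the thresholds for response and progression. The documents give no growth rates, and such growth would work against the study drugs. A gap of up to 28 days is permitted by Appendix 4 itself. No weight is placed on that argument.

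**Conclusion.** The point holds in limited form. The timing rules in 8.1 and 12.1 conflict with Appendix 4 and must be reconciled. The radiotherapy gap is real even when registration and first dose fall on the same day, and the adopted criteria do not clearly settle it.

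The figures of 12.6% and 13.9%, against 4.2%, are conditional on exactly one spurious confirmed response and a true rate of 5%. A reader might infer that the trial's type I error is actually inflated to that level. The documents do not support this, because they give neither the frequency of radiotherapy between scan and first dose nor the usual time from registration to dosing. What the figures do show is that one misattributed response roughly triples the false-positive risk (0.126/0.0416 = 3.0; 0.139/0.0416 = 3.3). That is reason enough for a small wording change before the data are read.

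**What to change.** 1. In 8.1 and 12.1, and in the section 10 schedule, time the baseline scan to within 28 days before Cycle 1 Day 1, in line with Appendix 4.
2. Require the scan to be taken after the last prior dose of systemic anticancer therapy.
3. State that a lesion irradiated or otherwise locally treated between the baseline scan and Cycle 1 Day 1 may not be a target lesion. If no other measurable lesion remains, judge measurability by Appendix 4's rule for previously treated lesions (demonstrated progression). A repeat scan alone does not restore it.
4. Limit item 3 to the period before first dose, so that it does not reach the palliative local therapy that section 9.3 allows on study. Leave the washout periods, on-study local-therapy rules and sample size unchanged.

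The cost is an occasional repeat screening scan or a small scheduling constraint and, rarely, a patient who no longer has measurable disease and so does not meet section 6.2 item 7.
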